#### **6.4.2 Definitions of serious adverse event**

A serious adverse event (SAE) is an AE occurring during any study phase (ie, run-in, treatment, washout, follow-up), that fulfils one or more of the following criteria:

- Results in death
- Is immediately life-threatening
- Requires in-patient hospitalisation or prolongation of existing hospitalisation
- Results in persistent or significant disability or incapacity
- Is a congenital abnormality or birth defect
- Is an important medical event that may jeopardise the patient or may require medical intervention to prevent one of the outcomes listed above.

For further guidance on the definition of a SAE, see Appendix B to the Clinical Study Protocol.

### 6.4.3 Recording of adverse events

#### Time period for collection of adverse events

Adverse Events will be collected from time of signature of informed consent and throughout the treatment period and the follow-up period (until Visit 7 or last study-related contact).

#### Follow-up of unresolved adverse events

Any AEs and laboratory abnormalities that are unresolved at the patient's last AE assessment in the study are followed up by the investigator for as long as medically indicated, but without further recording in the eCRF. AstraZeneca retains the right to request additional information for any patient with ongoing AE(s)/SAE(s) at the end of the study, if judged necessary.

#### Variables

The following variables will be collected for each AE:

- AE (verbatim)
- the date and time when the AE started and stopped
- maximum intensity
- whether the AE is serious or not
- investigator causality rating against the Investigational Product (yes or no)
- action taken with regard to investigational product
- outcome

The categories of intensity to be used in this study are:

- mild (awareness of sign or symptom, but easily tolerated)
- moderate (discomfort sufficient to cause interference with normal activities)
- severe (incapacitating, with inability to perform normal activities).

In addition, the following variables will be collected for SAEs:

- date and time AE met criteria for serious AE
- date Investigator became aware of serious AE
- AE is serious due to
- date of hospitalisation

- date of discharge
- primary/secondary cause of death
- date of death
- autopsy performed
- causality assessment in relation to study procedure(s)
- causality assessment in relation to other medication
- Description of AE.

It is important to distinguish between serious and severe AEs. Severity is a measure of intensity whereas seriousness is defined by the criteria in Section 6.4.2. An AE of severe intensity need not necessarily be considered serious. For example, nausea that persists for several hours may be considered severe nausea, but not a SAE. On the other hand, a stroke that results in only a limited degree of disability may be considered a mild stroke but would be a SAE.

### **Causality collection**

The Investigator will assess causal relationship between Investigational Product and each Adverse Event, and answer 'yes' or 'no' to the question 'Do you consider that there is a reasonable possibility that the event may have been caused by the investigational product?'.

For SAEs causal relationship will also be assessed for other medication and/or study procedures. Note that for SAEs that could be associated with any study procedure the causal relationship is implied as 'yes'.

A guide to the interpretation of the causality question is found in Appendix B to the Clinical Study Protocol.

### **Adverse Events based on signs and symptoms**

All AEs spontaneously reported by the patient, recorded in a diary card or reported in response to the open question from the study personnel: 'Have you had any health problems since the previous visit?', or revealed by observation will be collected and recorded in the eCRF. When collecting AEs, the recording of diagnoses is preferred (when possible) to recording a list of signs and symptoms. However, if a diagnosis is known and there are other signs or symptoms that are not generally part of the diagnosis, the diagnosis and each sign or symptom will be recorded separately.

### **Adverse Events based on examinations and tests**

The results from protocol mandated laboratory tests, ECGs and vital signs will be summarised in the clinical study report.

Deterioration as compared to baseline in protocol-mandated laboratory values, vital signs and other safety variables should therefore only be reported as AEs if:

- Fulfils any of the SAE criteria. This should be reported as a SAE.
- Reason for discontinuation of treatment with the investigational product. This should be reported as a Discontinuation AE (DAE).
- Investigator decides additional diagnostics and/or treatment is required because he/she considers deterioration of any of the safety variables to be clinically relevant. This should be reported as an AE (note, a repeat test showing the first abnormal result was not valid should not be reported as an AE).

If deterioration in a laboratory value/vital sign is associated with clinical signs and symptoms, the sign or symptom will be reported as an AE and the associated laboratory result/vital sign will be considered as additional information. Wherever possible the reporting investigator uses the clinical, rather than the laboratory term (eg, anaemia versus low haemoglobin value). In the absence of clinical signs or symptoms, clinically relevant deteriorations in non-mandated parameters should be reported as AE(s).

Any new or aggravated clinically relevant abnormal medical finding at a physical examination as compared with the baseline assessment will be reported as an AE.

#### **Adverse Events related to study procedures or the conduct of the study**

Signs and/or symptoms judged by the investigator to be clearly related to the conduct of the study or study procedures (eg, venepuncture; blood pressure and ECG measurement) are only to be reported as AEs if:

- Fulfils any of the SAE criteria. The should be reported as a SAE.
- Reason for discontinuation of treatment with the investigational product. The should be reported as a Discontinuation AE (DAE).
- Investigator decides additional diagnostics and/or treatment is required because he/she considers deterioration of any of the signs/symptoms/findings is clinically relevant. This should be reported as an AE (note, a repeat test showing the first abnormal result was not valid should not be reported as an AE).

#### **Symptoms of disease under study**

COPD symptoms or signs, such as cough, dyspnoea, sputum increased and wheeze (or terms considered synonymous with these) will not be recorded as AEs unless:

- the sign or symptom is serious according to the definition of an SAE (see Section 6.4.2), and/or

- the patient discontinues the investigational product due to the signs or symptoms, and/or
- the sign or symptom is new to the patient or not consistent with the patient's pre-existing COPD history (defined as within one year of screening (Visit 1.1)).

COPD exacerbations (see Section 6.4.10) that meet the SAE criteria as defined in Section 6.4.2 should be reported as SAEs.

### Disease progression

Disease progression can be considered as a worsening of a patient's condition attributable to the disease for which the investigational product is being studied. It may be an increase in the severity of the disease under study and/or increases in the symptoms of the disease.

Events, which are unequivocally due to disease progression, should be reported as an AE during the study.

### AEs with recommended follow-up activities

Results of abnormal liver function tests should be confirmed with a repeat test (via the central laboratory) as soon as possible, and within 48 hours, and the findings reported in the eCRF. Abnormal liver findings should be reported as AE(s) if in the investigator's judgment they meet the criteria. Abnormal liver function tests and hepatic AEs should be followed up and risk factors, signs and symptoms and diagnostic investigations recorded in the appropriate module provided in the eCRF.

AEs of infection should be followed up and risk factors, signs and symptoms and diagnostic investigations recorded in the appropriate module(s) provided in the eCRF.

### 6.4.4 Reporting of serious adverse events

All SAEs have to be reported, whether or not considered causally related to the investigational product, or to the study procedure(s). This includes SAEs occurring during any phase of the study, including run-in and follow-up periods where no investigational product is being given. All SAEs will be recorded in the eCRF.

If any SAE occurs in the course of the study, then investigators or other site personnel inform appropriate AstraZeneca representatives within one day ie, immediately but **no later than the end of the next business day** of when he or she becomes aware of it.

The designated AstraZeneca representative works with the investigator to ensure that all the necessary information is provided to the AstraZeneca Patient Safety data entry site **within one calendar day** of initial receipt for fatal and life threatening events **and within five calendar days** of initial receipt for all other SAEs. The AZ representative is required to access the AZ aware module within the WBDC system and trigger the email alert to the AstraZeneca Data Entry Site.

For fatal or life-threatening adverse events where important or relevant information is missing, active follow-up is undertaken immediately. Investigators or other site personnel inform AstraZeneca representatives of any follow-up information on a previously reported SAE within one calendar day ie, immediately but **no later than the end of the next business day** of when he or she becomes aware of it.

The investigator(s) and other site personnel will access the WBDC system and report SAE information by entering it into the relevant eCRF module. Once the Investigators or other site personnel indicate an AE is serious in the WBDC system, an automated email alert is sent to the designated AstraZeneca representative. If the WBDC system is not available, then the Investigator or other study site personnel reports a SAE to the appropriate AstraZeneca representative by telephone immediately. The AstraZeneca representative will advise the Investigator/study site personnel how to proceed.

The reference document for definition of expectedness/listedness is the IB for the AstraZeneca drug .

#### 6.4.5 Laboratory safety assessment

Blood and urine samples for determination of clinical chemistry, haematology, leucocyte counts and urinalysis will be taken at the times indicated in the Study Plan ([Table 3](#)).

Blood samples will be analysed at a central laboratory with the exception of leucocyte counts. Due to rapid degradation of neutrophils, leucocyte counts will be performed promptly in local laboratories within 2 hours (maximum 4 hours) of sample collection. Additional leucocyte (including neutrophil) counts will also be analysed at the central laboratory at intervals between receipt of sample and 72 hours after sampling to investigate leucocyte stability.

Urine will be tested locally using dipsticks. In addition, samples will be sent to the central laboratory for urine microscopy and quantitative measurements of total protein, albumin and creatinine if the local dipstick test for protein and/or blood is positive or if the urine sample appears abnormal on macroscopic examination, eg, if it is cloudy.

The central laboratory will provide all the materials required for blood and urine sampling. Instructions for labelling, storage and shipping will be detailed in the laboratory manual.

The laboratory variables to be measured are outlined in [Table 7](#).

**Table 7 Laboratory parameters**

Haematology	Clinical Chemistry	Urinalysis
B-Erythrocytes	S-Creatinine	U-Haemoglobin (dipstick)
B-Haemoglobin	S-Bilirubin (total)	U-Protein (dipstick)
B-Leucocyte count (absolute and differential count including neutrophils, basophils, lymphocytes, monocytes, eosinophils)	S-Alkaline phosphatase	U-Glucose (dipstick)
B-Platelet count	S-Aspartate Aminotransferase (AST)	U-Microscopy (if required, refer to Section 6.4.5)
	S-Alanine Aminotransferase (ALT)	U-Albumin (if required, refer to Section 6.4.5)
	S-Albumin	U-Total protein (if required, refer to Section 6.4.5)
	S-Protein (total)	U-Creatinine (if required, refer to Section 6.4.5)
	S-Potassium	
	S-Calcium (total)	
	S-Sodium	
	S-Glucose (non-fasted)	
	S-hsCRP	
	S-Urate	
	S-Urea	

For blood volume see Section 7.1.

#### 6.4.6 Physical examination

As detailed in Table 3, a physical examination will be performed at all visits except Visits 1 and 2.1. The assessment will be performed pre-dose at Visit 2.

At Visits 1.1, 6 and 7 a full physical examination will be performed and the following assessed: general appearance, skin, head and neck (including ears, eyes, nose and throat), lymph nodes, musculo-skeletal (including spine and extremities), cardiovascular, lungs and abdomen. At other visits, an examination of general appearance, cardiovascular system, lungs and abdomen is sufficient.

Height (screening only) will be measured in centimetres and weight (Visits 1.1, 2, 6 and 7) in kilograms. Measurements should be taken without shoes and using calibrated scales for all measurements. BMI will be calculated from the height and weight.

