### **Duration of treatment**

Patients who have given their informed consent at Visit 1 will attend a screening visit (Visit 1.1) for study screening procedures. Patients who fulfil the inclusion criteria and none of the exclusion criteria at this visit will enter the run-in period (minimum of 14 days, maximum of 21 days). At Visit 2 eligible patients will be randomised into the 4-week treatment period. Study visits will take place 2 days, 1 week, 2 weeks, 3 weeks and 4 weeks after randomisation (Visits 2.1 to 6). Patients will return to the clinic 1 to 2 weeks after stopping investigational product for a follow up visit (Visit 7). Patients will be asked to fill in a daily diary during the study (Visits 1 to 7). A new diary card will be given to the patient at each clinic visit.

The total duration of the study for a patient will be between 7 to 9 weeks.

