The doses to be used in this study have been selected following review of the data from the GSAD (D3550C00001) and GMAD (D3550C00007) and are predicted to minimise the number of subjects with circulating neutrophils remaining below a concentration of  $1.0 \times 10^9/L$  for more than 24 hours.

Reductions in neutrophil count may be associated with an increased risk of infections, particularly soft tissue infections. Patients will be regularly monitored by the investigators, including body temperature measurements.

For a more detailed risk benefit assessment of developing a CXCR2 inhibitor for COPD, see the AZD5069 IB.

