**Table 3 Table of study assessments**

Study Visit	Visit 1	Visit 1.1	Visit 2	Visit 2.1	Visit 3	Visit 4	Visit 5	Visit 6	Visit 7
Time (No. weeks/days)	Prior to Visit 1.1	14 – 21d prior to V2	Day 0	Day 2	1 week	2 weeks	3 weeks	4 weeks	3-18d after V6
Detail	Consent	Screening	Start treatment	Interim treatment visit	Interim treatment visit	Interim treatment visit	Interim treatment visit	End of treatment visit	Follow up
PK blood sampling			✓ k1			✓ k1	✓ k	✓ k1	
Leucocyte count including circulating neutrophils m		✓	✓ k1	✓	✓	✓ k1	✓ k	✓ k1	✓
Administer morning dose of investigational product in clinic (only applicable for PK sub study)			✓			✓ n		✓ n	
Dispense study drug			✓						
Drug accountability					✓	✓	✓	✓	
Blood sample for biomarkers			✓ d					✓	
Archive blood sample			✓ d					✓	
Adverse Event Questioning		✓	✓	✓	✓	✓	✓	✓	✓
Blood sample for Pharmacogenetics			✓ o						
Diary p	✓	→							
Telephone contact q					✓	✓	✓	✓	✓

a Informed consent must be obtained prior to any study-related procedures, restrictions or screening assessments. Adequate time must be given between consent and screening according to local requirements

b Inclusion and exclusion criteria to be assessed at applicable visits (where relevant at V1, V1.1 and V2)

c At Visits 1.1, 6 and 7 a full physical examination is require, at other visits a more brief examination is sufficient (see Section 6.4.6)

d Pre-dose assessments

e As well as body temperature measured at clinic visits, patients will be provided with an accurate thermometer and should record their oral body temperature twice daily (morning and evening) in their daily diary. Patient-recorded oral body temperature measurements will not be entered into the WBDC system. Patients will be instructed by site staff to contact the clinic if their body temperature increases above 38.1°C and this should be reported as an AE (see Section 6.4).

f Haematology analysis at the central laboratory will include leucocyte (and neutrophil) counts as exploratory variables at Visits 1.1, 2, 3, 4, 5, 6 and 7. Each single sample will be repeated analysed at the central laboratory (Quintiles); the first analysis will be upon receipt of the sample and then repeat

Revised Clinical Study Protocol  

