## 4.2 Exclusion criteria

Patients should not enter the study if any of the following exclusion criteria are fulfilled:

1. Any clinically significant disease or disorder (eg, cardiovascular, gastrointestinal, liver, renal, neurological, musculoskeletal, endocrine, metabolic, psychiatric, major physical impairment) which, in the opinion of the investigator, may either put the patient at risk because of participation in the study, or may influence the absorption, distribution, metabolism and excretion of drugs
2. Patients with active or latent tuberculosis (TB)
3. Patients with known Human Immunodeficiency Virus (HIV) or who belong to a high-risk group for HIV infection
4. Evidence of serum hepatitis or presence of hepatitis B surface antigen or hepatitis C antibodies
5. Patients with other latent or chronic infections (eg, recurrent sinusitis, urinary tract infection) or at risk of infection (surgery, trauma, significant infection within 90 days before Visit 2, history of skin abscesses or soft tissue infection within 90 days before Visit 2 or, in the opinion of the investigator, patients in regular contact with subjects who have active pulmonary TB [[Martineau et al 2007](#)]).
6. Exacerbation of COPD (defined as worsening in COPD requiring treatment with oral or parenteral antibiotics and/or oral or parenteral glucocorticosteroids (GCS) and/or hospitalization-related) which was not resolved within 30 days of Visit 2

7. Clinically significant lower respiratory tract infection not resolved 4 weeks prior to Visit 2, as judged by the investigator
8. Requirement for long term oxygen therapy
9. Patients who have received live or live-attenuated vaccine in the 2 weeks prior to first dosing (Visit 2)
10. Asthma and any current respiratory tract disorder other than COPD, which is considered by the investigator to be clinically significant or may influence the result of the study
11. Disease history suggesting reduced or abnormal immune function other than that related to COPD
12. Any clinically relevant abnormal findings in physical examination, clinical chemistry, haematology, urinalysis, vital signs or ECG at baseline (Visit 1.1), which, in the opinion of the investigator, may either put the patient at risk because of participation in the study, or may influence the results of the study, or the patient's ability to participate in the study
13. Active malignancy or neoplastic disease in the previous 12 months

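### Soft tissue infection is singled out as a risk of low neutrophils, but no skin examination is required between screening (Visit 1.1) and the end-of-treatment visit (Visit 6)

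*Protocol*

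**What the plan says.** Section 1.3 (benefit/risk) states the risk: "Reductions in neutrophil count may be associated with an increased risk of infections, particularly soft tissue infections". The monitoring it offers in reply is general: "Patients will be regularly monitored by the investigators, including body temperature measurements". Exclusion criterion 5 in Section 4.2 treats the same condition as relevant to eligibility, barring patients with a "history of skin abscesses or soft tissue infection within 90 days before Visit 2".

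Section 6.4.6 says that "a physical examination will be performed at all visits except Visits 1 and 2.1". It then sets two levels of examination. The full one is described as follows: "At Visits 1.1, 6 and 7 a full physical examination will be performed and the following assessed: general appearance, skin, head and neck", with further systems listed after that. For the remaining examined visits, which are Visits 2, 3, 4 and 5, it says: "At other visits, an examination of general appearance, cardiovascular system, lungs and abdomen is sufficient". Table 3 footnote c says the same in short form: "at other visits a more brief examination is sufficient". No other part of the protocol requires a skin examination between Visit 1.1 and Visit 6.

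Table 1 lists physical examination among the primary outcome variables. Under Section 6.4.3, a new or worsened clinically relevant finding on examination, relative to baseline, is to be reported as an adverse event.

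**The concern.** The study exists to obtain safety data beyond the 7.5 days of twice-daily dosing given so far to healthy volunteers (Section 1.2). Neutrophil reduction is the major effect seen in those studies (Section 1.3). The protocol names one kind of infection in particular, and the scheduled examination need not look at the organ where it would most readily be seen until dosing ends.

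Two things are at stake. The first is detection: a skin lesion without fever that the patient has not noticed, or has not thought worth mentioning, can appear and resolve between screening and Visit 6 and leave no examination record. The second is reference: the only required pre-dose skin finding is the one from Visit 1.1, made before the run-in.

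Blinding adds to this. Under Section 5.4.1, sites do not see leucocyte results from Visit 2 to Visit 7. They are told only of values above the upper limit, recalls and withdrawals, and some patients with normal counts are recalled at random. An investigator therefore cannot reliably direct a skin examination to patients with low counts. A routine examination, applied alike in all arms, is the only kind that is both even and blinded.

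**Working it through.** The plan gives no figure for this, so there is none to reproduce. The check lines up the examination content by visit and then measures the gap.

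**Required skin examination by visit (Section 6.4.6, Table 3 with footnote c)**

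| Visit | Timing | Physical examination | Skin required |
|---|---|---|---|
| 1.1 | Screening | Full | Yes |
| 2 | Day 0, pre-dose | Brief | No |
| 2.1 | Day 2 | None | No |
| 3 | Week 1 | Brief | No |
| 4 | Week 2 | Brief | No |
| 5 | Week 3 | Brief | No |
| 6 | Week 4, end of treatment | Full | Yes |
| 7 | Follow-up | Full | Yes |

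**Inputs**
- Run-in from Visit 1.1 to Visit 2: "minimum of 14 days, maximum of 21 days" (Synopsis, Duration of treatment).
- Treatment from Visit 2 to Visit 6: 4 weeks, nominally 28 days (Section 3.1).
- Planned patients: about 60 (Section 3.1).

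**Gap between required skin examinations, completing patient**

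Gap = run-in + treatment
- Shortest: 14 + 28 = 42 days
- Longest: 21 + 28 = 49 days

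The gap covers all dosing up to Visit 6.

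**Examinations inside the gap**
- Per patient: 1 pre-dose (Visit 2) + 3 on treatment (Visits 3, 4, 5) = 4, none with skin required.
- Across the study, if all 60 complete: 60 × 3 = 180 on-treatment examinations and 60 × 1 = 60 pre-dose examinations.

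These counts describe the schedule. They do not estimate how many lesions would be missed; the protocol gives no lesion rate from which to do so.

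**After adding skin at Visits 2 to 5**
- On treatment: 28 days ÷ 4 weekly visits (3, 4, 5, 6) = at most about 7 days between required skin examinations.
- Baseline: Visit 2 pre-dose, in place of a finding 14 to 21 days old.

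**The case against.** The strongest reply is that this is a choice of examination depth and that other safeguards carry the load. Much of that stands.

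- **No contradiction.** Section 6.4.6 and Table 3 footnote c agree. The brief examination is a minimum, and an investigator may look at the skin at any visit. A reader might infer that the protocol restricts the examination; its wording does not.
- **Section 1.3 promises less than a reader might infer.** It does not call soft tissue infection the main clinical consequence of the drug, and it does not promise skin monitoring. It singles out one kind of infection and undertakes regular monitoring in general, with temperature as the stated example. The protocol delivers that.
- **Detection does not rest only on what patients volunteer.** Section 6.4.3 collects events from an open question, diary cards and observation. Questioning takes place at every visit from 1.1 to 7, and staff telephone twice weekly. Patients take their temperature twice daily, and hsCRP is measured with the safety bloods.
- **A run-in lesion can usually be told from an on-treatment one.** A reader might infer the opposite from the missing Visit 2 skin finding. But adverse events are collected from consent with start date and time, and Section 12.2.3 classifies them by onset or worsening relative to first dosing. Only an unnoticed lesion, or one with no reliable onset date, is ambiguous.
- **Visit 2 is not empty.** Eligibility, including exclusion 5, is reassessed pre-dose. If the Visit 2 value is missing, Section 12.2.3 falls back on the latest pre-treatment measurement, so the Visit 1.1 examination is a defined, if older, comparator.
- **Early stoppers are seen sooner.** Section 5.8.1 asks them to attend Visit 6 with all its assessments.

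What the reply does not remove is that none of these measures is a skin examination. Questioning, diary and calls depend on the patient having noticed something. Temperature misses a lesion without fever. hsCRP does not point to a site. Infection follow-up modules start only once an infection has been recorded.

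**Conclusion.** The point holds as a mismatch between a named risk and the required examination. For a completing patient, no skin examination is required for 42 to 49 days, and none of the three on-treatment examinations before Visit 6 has to include skin. Physical examination is a primary variable, so a statement that soft tissue infection was not seen would rest mainly on patient report and on one look at the end of dosing.

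The size is modest. The other safeguards cover part of the risk, and what is left is chiefly the lesion that the patient has not noticed. Nothing here invalidates the trial or its analysis. It is a cheap and worthwhile improvement.

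Assumptions: nominal visit timing, a patient who completes 4 weeks of treatment, and investigators who do no more than the stated minimum at Visits 2 to 5.

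**What to change.** Add skin to the brief examination at Visit 2 (pre-dose) and Visits 3, 4 and 5. Change the list of systems in Section 6.4.6, align Table 3 footnote c, and add the item to the eCRF examination page for those visits. The named risk is then examined at baseline and weekly on treatment, in the same way in all three arms. The argument here supports adding skin only; lymph nodes and throat go beyond it.

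The cost is one line in each place and a minute or two within an examination already being done by the same staff. The small downside is a few more minor skin findings recorded, in active and placebo arms alike. No dosing, stopping or treatment rule changes.
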